Aims: (i) To replicate and extend R61 results supporting initial visual target engagement using the optimal R61 treatment, in a new and larger sample; and (ii) to determine if visual target engagement is associated with improvements in specific cognitive (i.e., visual working memory, visual learning and memory, reading) and social cognitive (*i.e.*, facial emotion recognition) outcomes, as well as with changes in functional capacity. Study design: The R33 will be a two parallel-arm RCT comparing the optimal R61 treatment to the control (ACCT) treatment. 100 subjects will be enrolled over 3 years, 50 from NKI and 50 from Rutgers. Visual and clinical outcome assessments will be conducted at baseline, and at intervals determined based on R61 results, including a 6-month follow-up (with attrition considerations and procedures identical to the R61 (see D.3). **Randomization:** Subjects will be randomly assigned, within site, to the optimal or control treatment in a ratio of 1:1. Treatment assignment for eligible subjects will occur after completion of baseline testing, to avoid bias. Assessments: Visual Targets and Cognitive, Social Cognitive, and Functional Capacity. No matter which intervention is used for the R33, visual tests will include both tests of CS, and both tests of PO used in the R61. See below (section D.6.c) for descriptions of the cognitive, social cognitive, and functional capacity measures. **Data analysis:** An intention to treat approach to data analysis will be used in this clinical trial. For all analyses. statistical significance will be defined as p < 0.05, unless specified otherwise. Bonferroni corrections will be applied to multiple testing, as appropriate. H1: The optimal R61 treatment will be more effective than the control treatment (ACCT) in improving CS and/or PO test scores (to be determined based on the R61 outcome). This will be tested using a linear mixed effects model in which the values of the target(s) at each time point are modeled as a function of treatment group (experimental, control), time, time x group, and potential moderators and mediators (e.g., age). We will use Akaike's Information Criterion (AIC) as the deciding metric to determine the optimal model to account for within-subject correlations between repeated measures (e.g., autoregressive of order 1, AR(1), which assumes stronger within-person correlation for measurements closer in time, or other structures). If the time x group interaction is significant, we will use model-based estimation procedures to estimate the magnitude of the effect. We will also explore differential effects of the treatment on CS vs. PO. H2: Improvements in visual processing, as observed in CS and/or PO (based on R61 results), will be related to changes on specific cognitive (i.e., visual working memory, visual learning and memory, reading), social cognitive (i.e., emotion recognition), and functional capacity measures. We will assess correlations between visual target scores and cognition, social cognition, and functional capacity, and also evaluate whether changes in the target(s) either mediate or moderate treatment effects on these outcomes. An approach and computational tool described by Hayes will be used to model any mediation and /or moderation effects, including indirect effects in models that involve mediation. Sample size determination: The sample size for the RCT in the R33 phase was selected to ensure sufficient power to detect medium effects of the experimental intervention on the target(s). For Aim 1 of the R33, 50 subjects per condition allows 80% power for a 2-tailed test with  $\alpha$ =0.05 to detect d=0.57. For Aim 2, with n=50 in the active perceptual training group, correlations of at least r=0.38 between changes in performance on target measures (CS and/or PO) and changes in cognitive, social cognitive, and functional capacity can be detected with 80% power using a 2-tailed test with  $\alpha$ =0.05. Also, for Aim 2, n=50 (i.e., active perceptual intervention only) allows for detecting a correlation of r=0.43 when making a strict Bonferroni adjustment for 3 outcomes (2-tailed  $\alpha$ =0.017), and r=0.51 when correcting for 15 outcomes (2-tailed  $\alpha$ =0.003). In accordance with instructions that the R33 "should not be powered as a strong test of clinical efficacy...", our focus on effect size is exploratory and not confirmatory. We will use our observed effect sizes to power a later RCT. D.5 Interventions

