# **D.6.b Visual Targets**

Contrast Sensitivity: CS functions will be obtained by presenting 5 horizontal sine-wave gratings at the following SFs: 0.5, 1, 4, 7, and 21 cycles per degree. Spatial frequency is the number of pairs or cycles of light and dark bars in 1 degree of visual angle, expressed as cycles/degree, with fewer pairs corresponding to lower SF. Each grating will be presented for 32 milliseconds. An up-and-down transformed response method will be used to obtain contrast thresholds with a criterion of 70.7% correct responses for each SF. The mean of 10 reversals will be used to obtain thresholds. Presentation of the different SF gratings will be interleaved in a random order. A spatial 2-alternative forced-choice procedure will be used. Gratings will be presented on either the right or left side of the screen, and the participant's task is to determine on which side the gratings appeared. Results will be plotted as CS (which is the reciprocal of threshold) vs. SF. Increased CS indicates better performance. Participants will be tested binocularly after being light-adapted to the background luminance of the display for 15 minutes. Test re-test reliability of this measure in a group of 15 controls and 31 patients (tested at the [name] lab at NKI) was an ICC of .76 at 0.5 cpd and .67 and 1 cpd. The test-retest reliability is weaker at the peak SF of 4 cpd (.25) and improves with higher SFs (ICC=.69 for 7 cpd and .57 for 21 cpd). The target variable is the average CS for the two LSFs (0.5 cpd and 1 cpd). We expect to see more of an effect of the remediation on LSF, but we will also assess CS at the other SFs, and specifically compare LSF

results to results at 7 cpd, which also has high reliability, to determine if effects are LSF-specific. VEP Contrast Responses: This VEP technique was developed by [name] and colleagues and has been used in studies of schizophrenia , autism^82, and glaucoma detection. The response measures are quickly and easily obtained, requiring no behavioral response from the participant. Parameters to be used have been optimized in our studies of schizophrenia. Steady-state VEPs are elicited to checkerboard patterns that are luminance-modulated sinusoidally (~12 Hz) with contrast increases in 7 discrete octave steps. Each

ure 4: VEP Contrast stimuli examples				
4%	8%	16%	32%	64%

[figure not shown]

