step is ~1.6 sec in duration to yield an entire contrastresponse function in less than 10 seconds (Fig. 4). The initial step has 0% depth of modulation (DOM) and this is followed by steps of 1, 2, 4, 8, 16, and 32% DOM. The set of steps is presented 10 times. In the contrast response function, as the DOM rises, the signal-to-noise ratio (SNR) increases from below a value of 1 to a value

greater than 1. To obtain the contrast at which SNR=1 (i.e., the contrast threshold), linear interpolation will be done for the first two consecutive contrasts (DOMs) at which SNR is less than one and then greater than one

. Test-retest reliability of low-contrast VEP responses in schizophrenia (N=32) is good (ICC=0.70; [name] lab, unpublished data). In addition, the 95% confidence regions for the 10 runs per person show good reliability within an individual. [name] has observed a within-subjects correlation of r=.41, (p<0.001; N=74) between indices from these VEP and psychophysical CS assessments.

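### The R33 H1 mixed model leaves the pre-randomisation baseline free to differ between arms, which is valid but gives up precision that a common-baseline or baseline-adjusted model would recover at almost no cost

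*Combined protocol and SAP*

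**What the plan says.** Section D.4 (R33 Phase, Data analysis) tests H1 with a linear mixed model, described as follows: "the values of the target(s) at each time point are modeled as a function of treatment group (experimental, control), time, time x group". The other terms are left open: "and potential moderators and mediators (e.g., age"). The test is the interaction: "If the time x group interaction is significant, we will use model-based estimation procedures to estimate the magnitude of the effect". The within-subject correlation structure is to be selected from the data: "We will use Akaike's Information Criterion (AIC) as the deciding metric to determine the optimal model". No baseline covariate, common baseline mean or site term is named. The coding of time and the visit at which the arms are compared are not stated either.

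On allocation, the same section says "Subjects will be randomly assigned, within site, to the optimal or control treatment in a ratio of 1:1" and "Treatment assignment for eligible subjects will occur after completion of baseline testing, to avoid bias".

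Section D.6.b gives reliability figures for the contrast sensitivity (CS) targets. For psychophysical CS, test-retest reliability "was an ICC of .76 at 0.5 cpd and .67 and 1 cpd", in 15 controls and 31 patients together. For the VEP measure: "Test-retest reliability of low-contrast VEP responses in schizophrenia (N=32) is good (ICC=0.70"). Reliability of the JOVI is described as good without a figure, and no reliability is given for the Ebbinghaus task.

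**The concern.** Because assignment follows baseline testing, the arms can differ at baseline only by chance. A free group effect at baseline asks the model to estimate a difference known to be zero in expectation. The interaction then subtracts the whole of the observed chance imbalance, where the efficient correction subtracts only the share that carries over to later visits.

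H1 is the R33 test of whether the selected training engages its visual target, and the plan looks to R33 to replicate the R61 result. The baseline scores needed for a sharper comparison are already collected, so the question is how much precision the written model leaves unused in a 100-patient trial recruiting over three years.

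**Working it through.** **Inputs.** From D.4: 50 per arm, two-sided alpha 0.05, d=0.57, 80% power. From D.6.b: ICCs of .76 and .67 (CS at 0.5 and 1 cycle/degree) and .70 (VEP). Assumption: these ICCs stand in for the baseline-to-follow-up correlation rho, which the documents do not give. Lower values are shown as sensitivity.

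**1. The plan's own figure.** Noncentrality = 0.57 x sqrt(50/2) = 2.85. A two-sample t test with 98 df gives 80.6% power (81.3% by the normal approximation). The stated 80% reproduces.

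**2. What the interaction estimates.** With time as visits, the group, time and time x group terms fit every arm-by-visit mean separately. With complete data, the contrast between a visit and baseline is then the difference in mean raw change, whichever covariance structure AIC selects.

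**3. Variances** (outcome SD 1 at each visit):
- as written: 2 x 2(1-rho)/50
- common baseline mean, or baseline as covariate: 2 x (1-rho²)/50
- ratio, adjusted to written: (1+rho)/2

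At rho=.70 these are 0.0240 and 0.0204, a ratio of 0.85. The ratio is below 1 for any rho below 1.

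**4. Power if d=0.57 is on the change-score SD.** The noncentrality becomes 2.85/sqrt((1+rho)/2), with 97 df.

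| rho | ratio | as written | adjusted | gain (points) | n per arm for equal precision |
|---|---|---|---|---|---|
| .76 | 0.880 | 80.6% | 85.3% | 4.7 | 44.0 |
| .70 | 0.850 | 80.6% | 86.4% | 5.9 | 42.5 |
| .67 | 0.835 | 80.6% | 87.0% | 6.5 | 41.8 |
| .60 | 0.800 | 80.6% | 88.4% | 7.8 | 40.0 |
| .50 | 0.750 | 80.6% | 90.3% | 9.7 | 37.5 |

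**5. Power if d=0.57 is on the raw-score SD.** The noncentrality is 2.85/sqrt(2(1-rho)) as written and 2.85/sqrt(1-rho²) adjusted.

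| rho | as written | adjusted | gain (points) |
|---|---|---|---|
| .76 | 98.3% | 99.1% | 0.9 |
| .70 | 95.4% | 97.7% | 2.3 |
| .67 | 93.5% | 96.7% | 3.2 |

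**6. More than two visits.** The R33 visits are not yet fixed, so this check assumes the R61 training schedule (baseline, then after 10, 20, 30 and 40 sessions), d on the change-score SD and large-sample power.
- Time as visits, compound symmetry, last-visit contrast: 81.3% rises to 87.7%, 87.1% and 86.0% at rho .67, .70 and .76. The gains match step 4.
- Time as a linear trend, compound symmetry: the test compares slopes, and the gain is about 3 to 8 points depending on the shape of improvement.
- AR(1) with the ICCs read as adjacent-visit correlations: baseline correlates with the last visit at only .67⁴=.20 to .76⁴=.33, and the gain is about 12 to 17 points on the last-visit or slope test.

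**7. Site.** A site main effect is constant within a patient and cancels from time x group. In the two-visit model at rho=.70, the interaction variance is 0.024 with and without it.

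**The case against.** The strongest reply is that nothing here is wrong. The model is a common one, it is unbiased under randomisation, and it delivers the stated power. That stands. A reader might infer that R33 is underpowered or that the 80% is in error, but the reproduced figure does not support this.

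A reader might also take a flat loss of 5 to 6 points as established. It is not, because it needs two facts that the documents omit.
- **The SD scale of d.** The R61 sample-size text gives a 95% interval of .02 to .91 for d=0.4 at 20 per group. On the change-score SD one would expect 0.4 ± 1.96 x sqrt(2/20 + 0.4²/80) = 0.4 ± 0.63, or -0.23 to 1.03. The stated half-width of 0.445 instead fits a raw-score SD: 0.2(1-rho) = (0.445/1.96)² gives rho of about .74. That interval is not centred on 0.4, so this is only a hint, but it points to the reading with the smaller gain.
- **The correlation.** The psychophysical CS ICCs mix controls with patients and are given for each frequency separately, while the target is their average. The R33 target may also be a perceptual organisation (PO) task, for which there is no figure.

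The authors could add that they prefer unadjusted change. Section D.3 does say so, but for the R61 go/no-go effect sizes and for change across two time points. D.4 gives no such reason for the multi-visit R33 model. They could also say that the covariate list is open. An unnamed covariate is not prespecified, however, and adding baseline as a covariate while it remains an outcome visit would not remove the free group effect.

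Finally, D.4 describes its interest in effect sizes as exploratory, so H1 should not be presented as a confirmatory efficacy test. Precision still matters, since H1 is tested at p<0.05 and the observed effects are meant to power a later trial.

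**Conclusion.** The point holds as one of efficiency. The written model is valid and its stated power is reproduced, but for a per-visit contrast with complete data its variance exceeds that of a baseline-constrained or baseline-adjusted model, the adjusted variance being (1+rho)/2 of the planned one.

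The size is conditional. With d on the change-score SD and rho equal to the ICCs, the gain is about 5 to 6 points (4.7 to 6.5), equivalent to about 42 to 44 patients per arm giving the precision that the written model gets from 50. It is about 10 points at rho=.5. With d on the raw-score SD, it is about 1 to 3 points at the ICCs. Describing the interaction as a raw-change comparison is exact only for time as visits and complete data.

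A reader might infer from the within-site randomisation that leaving site out contributes to the loss. It does not, because a site main effect cancels. Only a site x visit term could alter the contrast, and the documents give no figure for that. Including site is a separate, minor matter of matching the analysis to the randomisation.

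**What to change.** In D.4, H1, keep the mixed model and specify:
- time as visits, with group x post-baseline visit terms and no group effect at baseline, so that the arms share one baseline mean. Equivalently, take only post-baseline values as outcomes, with baseline and baseline x visit as covariates.
- site and site x visit as fixed effects, reflecting the stratified randomisation.
- the H1 test as the group contrast at a named visit.

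State also the SD on which d=0.57 is expressed and the pre-post correlation assumed, so that the gain can be calculated. R61 will supply estimates of that correlation for all four target tasks before R33 starts.

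The cost is a sentence or two in the analysis plan and a few degrees of freedom out of 98. No new data, visits or patients are needed.

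### As worded, the R33 H1 model permits mediators beside the time x group term that decides H1, so that term could stop estimating the total effect of randomised assignment

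*Combined protocol and SAP*

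**What the plan says.** All of this is in the Data analysis and Sample size paragraphs of D.4 (R33 Phase), unless another section is named.

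- **The H1 test.** "This will be tested using a linear mixed effects model in which the values of the target(s) at each time point are modeled". This is the only model given for H1. Its listed terms are "treatment group (experimental, control), time, time x group, and potential moderators and mediators (e.g., age"). Nothing says that H1 is tested first without mediators, that mediators enter only a secondary model, or which variables they would be.
- **The deciding term.** "If the time x group interaction is significant, we will use model-based estimation procedures to estimate the magnitude of the effect".
- **Analysis principle and error level.** "An intention to treat approach to data analysis will be used in this clinical trial", and "statistical significance will be defined as p < 0.05, unless specified otherwise".
- **Power.** With 50 per arm and a two-sided alpha of 0.05, the plan claims 80% power "to detect d=0.57".
- **Mediation elsewhere.** Under H2 the plan will "also evaluate whether changes in the target(s) either mediate or moderate treatment effects on these outcomes", using a published mediation and moderation tool. There the visual targets are the candidate mediators, and cognition, social cognition and functional capacity are the outcomes.
- **Links between the two targets.** D.1 reports that lower peak CS went with poorer contour integration (r=.69, N=17), and that pilot structural equation models found CS mediating the relation between abnormal VEPs and PO. D.3 plans to ask whether UE, by acting on CS, cascades to PO. D.4 measures both CS tests and both PO tests whichever treatment is carried forward.

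**The concern.** H1 asks whether assignment to training improves the target. Randomisation protects that comparison only while the model conditions on things fixed before assignment. Conditioning on something that training changes removes from time x group whatever part of the effect runs through it. It also exposes the remainder to any unmeasured cause shared by the mediator and the target, which can bias it in either direction.

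The R33 result has two uses that need the total effect. Section B relies on the R33 as the replication that would show the R61 findings are not spurious. Sections B and D.4 say that its observed effect sizes will power a later trial. A direct-effect estimate would serve neither. Because the mediators are not listed, the H1 result could also depend on which ones an analyst chose to enter.

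**Working it through.** **Inputs.** From D.4: 50 per arm, two-sided alpha 0.05, d=0.57, stated power 80%. Not in the documents, and therefore assumed: the share m of the effect that runs through a mediator, and the mediator-outcome slope b.

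**1. Reproduce the plan's figure.** Power is approximately Φ(d·√(n/2) − 1.96). With n=50, √25 = 5, so 0.57×5 − 1.96 = 0.89 and Φ(0.89) = 0.813. The two-sample t-test gives 0.806, with a detectable d of 0.566 at 80% power. The stated figure stands. It is for an unadjusted two-group comparison, that is, the total effect.

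**2. What the coefficient becomes.** Let a be the effect of treatment on the mediator. Then total effect = direct effect + a·b. With the mediator in the model, the treatment term targets only the direct part, d_direct = 0.57×(1 − m).

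**3. Hypothetical sizes.** The normal and t columns hold the residual SD at 1. The last column simulates change scores (5,000 runs per setting) with M = aT + e1, Y = 0.57(1 − m)T + bM + √(1 − b²)·e2 and a = 0.57m/b. This credits the model with the outcome variance that the mediator explains.

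| m | d_direct | Normal | t-test | Simulated, b=0.3 / b=0.5 |
|---|---|---|---|---|
| 10% | 0.513 | 0.727 | 0.719 | not run |
| 25% | 0.428 | 0.570 | 0.562 | 0.565 / 0.677 |
| 50% | 0.285 | 0.296 | 0.292 | 0.266 / 0.341 |
| 75% | 0.143 | 0.106 | 0.109 | not run / 0.114 |

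In the same simulations, the model without the mediator recovered about 0.57 with power 0.80 to 0.81. Taking the t-test and simulated values together, power is roughly 56-68% at m=25% and 27-34% at m=50%.

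**4. When time x group moves in a longitudinal model.** One balanced data set was simulated with 100 participants and two time points. The direct effect was 0.30 and the time-varying mediator had a=0.6 and b=0.45, so the true total was 0.30 + 0.6×0.45 = 0.57.

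- Group, time and time x group only: estimate 0.731 (SE 0.179).
- Adding age as a main effect: 0.731, unchanged.
- Adding the time-varying mediator: 0.467 (SE 0.130).

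The drop, 0.731 − 0.467 = 0.264, is close to the built-in indirect effect of 0.27. One data set illustrates the mechanism and does not estimate its size in this trial. A baseline main effect leaves the deciding term alone; a time-varying mediator does not.

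**5. Is there a realistic candidate?** D.1 and D.3 treat CS as a possible route to PO, and D.4 measures both repeatedly. If PO is the H1 target, CS is a time-varying variable that training may change.

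**The case against.** The strongest reply is that this is loose wording for covariates. The only example is age, which training cannot change. The word potential leaves open whether any mediator is entered. The plan's main mediation chain runs from training through the visual target to cognition and function, and it already has its own analysis under H2. No section says that CS would be entered in an R33 model for PO. All of this stands, and it limits what can be claimed.

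Four stronger readings are tempting, and the documents do not support them:

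- *H1 is adjusted for variables that training changes.* The text permits this but does not specify it.
- *The H1 estimate is necessarily pulled toward zero.* It moves only if the mediator is time-varying or interacts with time or group, and confounding could push it either way.
- *The stated power is wrong.* It reproduces.
- *The H2 sentence is a second instance of the problem.* It is a separate analysis in which the target is the mediator, and it is the proper place for such work.

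A direct contradiction of intention to treat is also arguable rather than shown. D.4 does not define the term, which often refers only to who is analysed and in which arm.

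D.4 calls the focus on effect size exploratory and not confirmatory, which lowers the stakes. It does not remove the problem, because H1 still has a p < 0.05 test and a power statement. Nothing elsewhere in the plan settles the ambiguity, and an analyst who followed the sentence could enter a mediator.

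**Conclusion.** The point holds as a defect in what the H1 model permits. The one model stated for H1 allows mediators beside the term that decides it. A time-varying mediator, or one interacting with time or group, would turn time x group into a direct effect open to mediator-outcome confounding, a different quantity from the one that was powered. CS with PO as the target is a realistic route to this, so more than tidiness is at issue.

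The size cannot be derived from the documents, because no mediator and no mediated share are given. The figures of d about 0.43 with power of roughly 56-68%, and d about 0.29 with power of roughly 27-34%, are hypothetical. They rest on assumed shares of 25% and 50%, assumed slopes of 0.3 and 0.5, and a change-score comparison rather than the full mixed model. At an assumed 10%, the loss is smaller (power about 0.72 to 0.73). If only baseline variables such as age are entered as main effects, this problem does not arise.

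**What to change.** In D.4, H1, delete the reference to mediators. State that H1 is tested with group, time, time x group and pre-specified pre-randomisation covariates only, and list them: site, because randomisation is within site, and for example age. Naming the list in advance also removes the choice of terms after the data are seen.

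Examine baseline moderators that interact with group or with time x group in separate exploratory models. Otherwise the time x group term becomes the effect at the moderator's zero value. Confine any mediation analysis, including one of CS as a route to PO, to a separately labelled analysis such as that under H2.

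The cost is one sentence of analysis wording. No data, visits or participants are affected, the sample size stays as it is, and the stated power then refers to the effect being tested.

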# D.3 R61 Phase

Aims: (i) To evaluate the effects of UE and CIT on the CS and PO targets, respectively; (ii) to determine if the criterion for continuing to the R33 phase is met; and (iii) if the criterion is met, to determine the most effective intervention condition and optimal duration of treatment, to inform the R33 study design.

Study design: 80 subjects will be enrolled in this study: 20 per arm. 40 will be recruited at each site (Rutgers and NKI). The intervention will continue for 40 sessions, with targets assessed before training, after every 10 sessions, and at 6 months post-training for a total of 6 visual assessments. With 3 sessions per week, the intervention will take between 13-14 weeks. Each site will enroll ~ 2 participants/month, beginning after the first half of Y1, which is similar to what Keefe et al. estimated as a "reasonable rate of recruitment for a largescale efficacy trial" of cognitive remediation. Because, at the 6-month follow-up, nearly all patients are expected to still be in the partial hospital program, or an outpatient program (at Rutgers), or on inpatient units at the Rockland Psychiatric Center (RPC) or NKI, we expect attrition to be minimal. However, several methods, including monthly phone calls (see Recruitment and Study Timeline), will be used to maximize retention. For the R61 and R33, training sessions will be run in small groups by front-line staff who have already received training in these interventions, or whom we will train, with no more than a 3:1 participant:staff ratio. Randomization: Subjects will be randomly assigned, within site, to one of the 4 conditions (UE&ACCT, CIT&ACCT, UE&CIT and ACCT&ACCT) in a ratio of 1:1:1:1. The treatment assignment will be made after a subject has met all entry criteria and completed baseline testing, to avoid bias.

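### The R33 Aim 2 change-change correlations name no site term, so site gaps in mean change on both measures could inflate or mask the within-site link; adding site costs almost nothing

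*Combined protocol and SAP*

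**What the plan says.** Section D.4 (R33 Phase, Data analysis, H2) describes the test of the link between target engagement and higher-level outcomes: "We will assess correlations between visual target scores and cognition, social cognition, and functional capacity". It adds models of whether target change mediates or moderates treatment effects. The H2 statement and the sample-size text show that changes are meant.

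The Aim 2 sizing in D.4 is for one plain correlation inside one arm: "with n=50 in the active perceptual training group, correlations of at least r=0.38 between changes in performance on target measures" and cognitive, social cognitive and functional change "can be detected with 80% power using a 2-tailed test with" alpha 0.05. Corrected levels follow: "n=50 (i.e., active perceptual intervention only) allows for detecting a correlation of r=0.43 when making a strict Bonferroni adjustment" for 3 outcomes (alpha 0.017), and "r=0.51 when correcting for 15 outcomes" (alpha 0.003).

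Site enters the design. D.4 enrols 50 patients at each of two sites, and "Subjects will be randomly assigned, within site, to the optimal or control treatment". It enters no analysis: the H1 mixed model lists group, time, their interaction and possible moderators and mediators with age as the example, and H2 lists no covariates.

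On setting, section D.3 (R61, which D.4 refers back to for attrition) expects that at the 6-month follow-up nearly all patients will be in the "partial hospital program, or an outpatient program (at Rutgers), or on inpatient units at the Rockland Psychiatric Center (RPC) or NKI".

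**The concern.** Randomising within site balances site between arms. That protects the H1 comparison, where omitting site mainly costs precision. It does not protect a correlation computed inside one arm, where both variables are observed. There, site is an ordinary potential common cause. If patients at one site change more on the target and also on the outcome, because of setting, case mix or staffing, pooling produces a correlation that exists within neither site. If the gaps run in opposite directions, pooling hides a real one.

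The H2 link is what R33 is for. The Significance section cites the funder's instruction that this phase should test the link between target engagement and functional outcome. D.4 says that the observed effect sizes will be used to power a later RCT, so a distorted r would carry into that design.

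**Working it through.** **Inputs.** From D.4: 50 active-arm patients; 50 patients per site with 1:1 allocation within site, hence about 25 active-arm patients per site; two-sided alpha 0.05, 0.017 or 0.003; 80% power; stated r of 0.38, 0.43 and 0.51. The site gaps in mean change are assumptions.

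**1. The plan's own figures.** By Fisher z, detectable r = tanh[(z(1−α/2) + z(0.80)) / √(n−3)]. With n=50 and alpha 0.05 this is tanh[(1.960 + 0.842)/√47] = 0.387. At 0.017 and 0.003 it is 0.439 and 0.505. In the other direction, the stated r of 0.38, 0.43 and 0.51 have power of 79.1%, 78.5% and 81.7% by simulation of the exact distribution of r. All are within 2 points of 80%, so the figures are those of a single correlation with no covariate.

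**2. What pooling does.** Take two equal sites, gaps dx and dy in mean change (in within-site SD units), and within-site correlation r_w:

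pooled r = (r_w + dx·dy/4) / √[(1 + dx²/4)(1 + dy²/4)]

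The numerator shifts only through the product dx·dy, so a gap in one measure cannot create a correlation.

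**3. No within-site link, equal gaps in the same direction.** For example, at 0.5 SD: 0.0625/1.0625 = 0.06. Rejection rates are simulated, n=50.

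| Gap in both (SD) | Pooled r | α=0.05 | α=0.017 | α=0.003 |
|---|---|---|---|---|
| 0.3 | 0.02 | 5.2% | 1.8% | 0.3% |
| 0.5 | 0.06 | 6.8% | 2.6% | 0.55% |
| 0.8 | 0.14 | 16% | 7.6% | 2.1% |
| 1.0 | 0.20 | 29% | 16% | 5.4% |

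With site partialled out, the rate stays at the nominal level in every row.

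**4. Within-site r of 0.38, equal gaps in opposite directions.** For example, at 0.8 SD: (0.38 − 0.16)/1.16 = 0.19.

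| Gap in both (SD) | Pooled r | Power, pooled | Power, site-adjusted |
|---|---|---|---|
| 0.3 | 0.35 | 72% | 78% |
| 0.5 | 0.30 | 56% | 78% |
| 0.8 | 0.19 | 24% | 78% |
| 1.0 | 0.10 | 9% | 78% |

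**5. A gap of 0.8 SD in one measure only.** With r_w = 0 the rejection rate stays at about 5%. With r_w = 0.38 the pooled r is 0.38/√1.16 = 0.35 and power is 72%.

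**6. Cost of a site term.** One covariate changes n−3 to n−4. The detectable r is tanh(2.802/√46) = 0.391 at alpha 0.05, 0.443 at 0.017 and 0.509 at 0.003. Power at r=0.38 falls from 79.2% to 78.5% (simulated).

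**The case against.** The strongest reply is that no bias has been shown. Care setting speaks first to levels, and stable level differences cancel in change scores. A spurious link needs gaps in mean change on both measures, and the documents report none. On the plan's own scale the larger assumed gaps are extreme: 0.8 SD between sites, inside one arm and on both measures, would exceed the d=0.57 treatment effect that R33 is sized to detect. At 0.57 SD on both, the pooled r is 0.075 and the rejection rate about 8%. D.4 also plans Bonferroni corrections where appropriate, which lowers the absolute rates. Section D.6 standardises scripts, stimulus parameters and calibration across sites, and D.6.a provides common rater training with reliability thresholds. D.2 sets shared entry criteria. The contrast in setting is not clean either: D.10 says that both sites have on-site clinics, and the R61 sample-size text describes most participants as long-stay inpatients or partial hospital patients. All of this stands. It limits the plausible size, but does not make the two sites' patients alike or supply the missing term.

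A second reply is that between-site covariance belongs to the link H2 asks about, so removing it discards signal. This fails. With two sites that component rests on one contrast, and it cannot be separated from care setting.

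A third reply is that D.4 calls its focus on effect size exploratory. That is true and lowers the urgency, but the same paragraph commits the estimates to powering a later trial.

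A reader might also carry the n=50 figures over to the mediation models. The documents do not support that. Those models concern treatment effects and so need both arms. Their mediator-to-outcome path is likewise not randomised, which is reason to include site, but the calculations above do not size the problem there.

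**Conclusion.** The point holds as a conditional one. H2 is specified and sized as an unadjusted correlation over two sites that the documents describe as differing in care setting, and randomisation does not protect it. Site gaps in mean change on both measures could inflate or mask the within-site link; a gap in one measure only attenuates it. The effect on false positives is negligible near 0.3 SD, modest at 0.5 SD (about 7% at alpha 0.05) and serious only from about 0.8 SD. Masking bites sooner: power is 56% instead of 78% at opposite gaps of 0.5 SD. These figures assume equal sites, normally distributed changes and equal gaps on both measures.

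Three stronger readings are tempting and unsupported. The first is that the H2 estimate will be biased: no site-level change data exist in the documents. The second is that the stated detectable correlations are wrong: they reproduce. The third is that the plan rules out a site term: its absence is inferred from silence and from the unadjusted power basis, and nothing forbids one. The case for change is that the gaps will be unknown when the plan is fixed and the safeguard is nearly free.

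**What to change.** In D.4, under H2, state that each change-change association will be estimated as a partial correlation given site, or equivalently by regressing outcome change on target change with site as a fixed effect. Report the two within-site estimates beside it descriptively; about 25 patients each is too few for separate tests. Include site as a covariate in every equation of the two-arm mediation models. In the Aim 2 sample-size text, give the detectable r with site included.

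The cost is a sentence or two in the plan and one degree of freedom. The detectable r at 80% power moves from about 0.387 to 0.391 at alpha 0.05, and by about 0.004 at each corrected level. No new data are needed, because site is the randomisation stratum.
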